to attend clinic visits (days 1, 3, 8, 15 and 20) and overnight sleep lab visits (days 1, 2, 20 and 21). On every day of the treatment period, the subject will complete the CSD-M. At sleep lab visits, the subject will undergo PSG and complete the Digit Symbol Substitution Test (DSST), Karolinska Sleepiness Scale (KSS), and Profile of Mood States-Brief Form (POMSTTM-Brief). At clinic visits, subjects will complete: the Columbia-Suicide Severity Rating Scale (C-SSRS), Hospital Anxiety and Depression Scale (HADS); will undergo clinical laboratory testing, drug/alcohol screening, vital sign measurements, 12-lead electrocardiogram and a neurological exam. Adverse events and concomitant medications will be assessed. Blood samples for sparse pharmacokinetic (PK) analysis will also be collected during clinic visits.

During the washout period, (days 22 and 23) subjects will receive placebo treatment in a single-blind manner and undergo PSG testing. An end of treatment (EOT) clinic visit will be conducted on day 24.

The subject will return home and continue to complete the CSD-M [REDACTED] and will return for a clinic visit approximately 1 week after the last double-blind treatment dose to perform end of study (EOS) evaluations. A follow-up phone contact to assess safety will be done approximately 1 week after EOS visit.

Planned Number of Subjects (including sample size rationale):

Planned total number of randomized subjects is approximately 150 (~50 per treatment group) to ensure at least 30 subjects per group complete treatment.

A sample size of 30 subjects per treatment group has >80% power for detecting a statistically significant difference vs. placebo of 30 minutes (SD=45 minutes) for WASO, based on a 1-sided 2-sample t-test at 5% significance level.

Criteria for Inclusion/Exclusion:

Inclusion Criteria:

Participants are eligible if they meet all the following criteria:

1. Male or female, 18-64 years of age with a body weight of 50-100 kg (110-220 lbs) and a body mass index (BMI) of 18-32 kg/m².
2. Otherwise healthy as determined by medical evaluation that includes: medical history, physical examination, neurological exam, laboratory tests, vital signs, and cardiac monitoring.
3. History of moderate or severe alcohol use disorder (AUD) categorized based on DSM-5 criteria, as follows:
 - Moderate as defined by presence of 4-5 of the 11 criteria
 - Severe as defined by the presence of ≥ 6 of the 11 criteria.

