15. Any history and/or current evidence of other medical (e.g., cardiac, respiratory, gastrointestinal, renal, malignancy other than basal cell carcinoma), neurological, or psychiatric conditions that, in the opinion of the investigator, could affect the subject's safety or interfere with the study assessments.

Prior/Concomitant Therapy

16. Use of any medication that affects sleep and/or wake function during the week before starting the Consensus Sleep Diary-Morning (CSD-M).
17. Subjects currently undergoing treatment of other addictions in addition to alcohol (eg. nicotine, cocaine, opioids, methamphetamine, etc. or other substances)
18. Excessive caffeine consumption \geq 300 mg/day (e.g., approximately three 6-oz cups of caffeinated coffee, or three 12-oz caffeinated sodas, or three 8-oz caffeinated tea beverages).

Prior/Concurrent Clinical Study Experience

19. Dosing in a clinical drug study during the 30 days (or 5 half-lives of investigational drug treatment, whichever is longer) preceding the initial dose of study drug dispensed in this study.
20. Subjects previously exposed to V117957.
21. Subjects with hypersensitivity to V117957 or any of its ingredients.

Diagnostic assessments

22. Positive urine drug screen or alcohol screen at any time during the study, except for cannabis on a case-by-case basis.
23. History of drug use disorder over the past year, other than alcohol/nicotine/caffeine/cannabis.

Other Exclusions

24. Unwillingness to avoid napping during each confinement when not undergoing PSG
25. Scheduled for surgery during the study.

- | |
|---|
| 26. Plans to travel across more than 3 time zones in the 2 weeks before screening, or during study participation.
27. Night or rotating shift worker.
28. The investigator believes the subject to be unsuitable for reason(s) not specifically stated in the exclusion criteria (ie, subjects whose history may indicate a likelihood of relapse). |
|---|

Test Treatment, Dose, and Mode of Administration:

All doses will be administered with water in the evening at bedtime, at least 1 hour after the last meal of the day, for up to 21 consecutive nights during the double-blind treatment period.

- V117957 1 mg, tablet, oral administration
Subjects assigned to 1 mg V117957 will take 2 tablets, each containing 0.5 mg V117957
- V117957 2 mg, tablet, oral administration
Subjects assigned to 2 mg V117957 will take 2 tablets, each containing 1 mg V117957

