Reference Treatment, Dose, and Mode of Administration:

All doses will be administered with water in the evening at bedtime, at least 1 hour after the last meal of the day, for up to 23 consecutive nights (21 nights during the double-blind treatment period to subjects assigned to placebo and for 2 nights during the washout period to all subjects).

- Placebo tablet, oral administration
Subjects assigned to placebo will take 2 placebo tablets

Concomitant Medication:

Medications for chronic conditions, such as antihypertensives, lipid lowering agents, acetaminophen, NSAIDs and vitamins, are allowed as long as the subject is on a stable regimen throughout their study participation.

Duration of Treatment and Study Duration:

Total study duration is approximately 59 days.

Screening period is up to 21 days; double-blind treatment period is 21 days; washout period is 3 days; and the follow-up (safety) period is approximately 14 days.

Study Procedures:

Screening period (up to 21 days):

The screening period is 21 days prior to randomization. Screening activities consist of demography, medical and medication history, physical and neurological exam, 12-lead electrocardiogram (ECG), and vital sign measurements (systolic/diastolic blood pressure, pulse rate, respiratory rate, and oral temperature), pulse oximetry (SpO2), drug and alcohol screen, hepatitis B and C screen, serum pregnancy test (females only), FSH test for post menopausal women, clinical laboratory assessments, inclusion/exclusion criteria evaluation (including completion of the C-SSRS), the CSD-M including assessment of insomnia [REDACTED]. If the CSD-M shows insomnia the subject should be scheduled for PSG testing to confirm insomnia.

Double-blind treatment period:

Treatment activities consist of a urine pregnancy test (females only), C-SSRS, HADS, drug and alcohol screen, neurological exam, ECG, vital sign measurements, AEs and concomitant medications, CSD-M, [REDACTED] PSG tests – 2 at the beginning and 2 at the end of the period, DSST, KSS, POMS-Brief, clinical laboratory assessments, sparse PK sampling and receive study drug treatment. During the double-blind treatment period subjects will be dosed in the sleep lab and will take medication home with them for daily nighttime dosing. Subjects will return to the clinic on days 8, 15 and 20 for study procedures.

Washout period:

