For CSD-M sleep diary data which will be processed into weekly data, the statistical analysis to compare change from baseline of V117957 versus placebo will be performed by using a mixed model with repeated measures (MMRM) with factors of age group, treatment, visit (first 2 nights, week 1, week 2, and week 3), and treatment-by-visit interaction as fixed effects, and baseline measurement as a covariate. 90% confidence intervals (CIs) and P-values comparing placebo and each V117957 dose will be summarized. Plots of the least squares (LS) mean change from baseline and 90% CIs, will be produced by treatment group and visit.

[REDACTED]
[REDACTED]
Pharmacodynamic Analyses 
Listings, tables, and figures of next day residual effects measured by DSST, KSS, and POMS-Brief will be based on the full analysis population. Descriptive statistics will be tabulated by treatment and presented graphically. The analysis will be performed similarly as outlined above for the primary endpoint.

[REDACTED]
Safety Analyses 
All safety data [REDACTED] will be listed for subjects in the enrolled and randomized safety populations.

AEs will be categorized into preferred terms and associated system organ class (SOC) using the Medical Dictionary for Regulatory Activities (MedDRA). Treatment-emergent AEs (TEAEs) will be defined as AEs that start after or increase in intensity after the first dose of study drug. TEAEs will be summarized by presenting the incidence of AEs for each treatment group by the MedDRA preferred term, nested within System Organ Class for the safety population. Medical history will be coded to MedDRA terms. Coded medical history terms will be summarized for all subjects in the randomized safety population.
[REDACTED] Concomitant and prior medications will be coded using the latest version of the WHO-DD and presented in tables and listings.
Interim Analysis 
After approximately half of the planned subjects have completed the end-of-study visit, an interim analysis may be performed [REDACTED] The results of the analysis will not be conveyed to the study team or to the clinical sites.

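### Does the diary model's separate level for the first 2 nights, alongside an undefined week 1, distort the diary treatment comparisons?

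*Combined protocol and SAP*

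**What the plan says.** The diary analysis is in the Synopsis under Secondary Efficacy Analyses. The data are introduced by "For CSD-M sleep diary data which will be processed into weekly data". The model has age group, treatment, "visit (first 2 nights, week 1, week 2, and week 3), and treatment-by-visit interaction as fixed effects", with the baseline value as a covariate. On reporting, it says that "90% confidence intervals (CIs) and P-values comparing placebo and each V117957 dose will be summarized". Plots of least squares mean change with 90% intervals "will be produced by treatment group and visit".

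Three other places fix the calendar:

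- **Dosing.** It runs "for up to 21 consecutive nights during the double-blind treatment period" (Test Treatment, Dose, and Mode of Administration).
- **Diary.** "On every day of the treatment period, the subject will complete the CSD-M" (Study Design).
- **Visits.** Sleep-lab nights fall on days 1, 2, 20 and 21, and clinic visits fall on days 1, 3, 8, 15 and 20 (Study Design).

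No visible sentence lists the nights in each level, names the visit or average to which the P-values belong, or names a covariance structure. Blacked-out blocks follow the diary paragraph directly.

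**The concern.** Three 7-night weeks already use all 21 treatment nights. A fourth level for nights 1-2 therefore either counts those nights twice or shrinks week 1 to five nights. Both readings are plausible: clinic visits on days 8 and 15 suit weeks of seven nights, while the sleep-lab stay on nights 1-2 suits a week 1 that starts at night 3.

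The contrast is also open. With a treatment-by-visit interaction in the model, the dose-placebo difference could be reported at each visit, at week 3, or as an average over the levels. Statistical software commonly forms that average with equal weights. Nights 1-2 would then count far more than their share of treatment. An effect confined to the first nights would be overstated, and one that starts later would be understated. An effect that changes over time is a real question here, since polysomnography is done at both the start and the end of treatment.

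**Working it through.** **The plan's own figure.** The visible text gives no figure for the diary model. Its only power statement concerns polysomnographic WASO: 30 per group, difference 30 minutes, SD 45, one-sided 5%. The noncentrality is 30 / (45 × √(2/30)) = 2.58, which gives 81.8% power by the noncentral t distribution (82.6% by the normal approximation). The stated figure of more than 80% reproduces, and nothing below bears on it.

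**Weight on nights 1-2 in an equal average of four levels.**

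- Week 1 = nights 1-7: 1/4 + (1/4)(2/7) = 32.1%.
- Week 1 = nights 3-7: 1/4 = 25.0%.
- Plain 21-night mean: 2/21 = 9.5%.

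**What that would do to an estimate.** Let the effect be *a* on nights 1-2 and *b* on every later night. The four-level average then departs from the 21-night mean by (0.3214 − 0.0952)(a − b) = 0.226(a − b) if week 1 overlaps, or (0.2500 − 0.0952)(a − b) = 0.155(a − b) if it does not. The table uses assumed effects in minutes. The value 30 is borrowed from the WASO sample-size statement, because the documents give no diary effect.

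| Nights 1-2 / later | Four-level average, week 1 = 1-7 | Four-level average, week 1 = 3-7 | 21-night mean |
|---|---|---|---|
| 30 / 0 | 9.6 | 7.5 | 2.9 |
| 0 / 30 | 20.4 | 22.5 | 27.1 |
| 30 / 10 | 16.4 | 15.0 | 11.9 |
| 10 / 30 | 23.6 | 25.0 | 28.1 |
| 30 / 30 | 30 | 30 | 30 |

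The first two rows are extremes, and the last shows that a constant effect is not distorted.

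**What happens with one contrast per visit.** The levels estimate:

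- first 2 nights: *a* on both readings;
- week 2 and week 3: *b* on both readings;
- week 1: (2/7)a + (5/7)b if nights 1-7, or *b* if nights 3-7.

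Only week 1 depends on the definition, and the two versions differ by (2/7)(a − b). With 30 / 10 that is 15.7 against 10, a gap of 5.7 minutes. With 30 / 0 it is 8.6 against 0. Each is a correct answer to its own question. No averaging over levels is involved.

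**Does overlap break the model?** No. If week 1 is nights 1-7, its mean still contains five nights that are not in the first level. The two responses are correlated but neither determines the other. An unstructured covariance for four levels has 4 × 5 / 2 = 10 parameters, a modest number for about 150 randomized subjects.

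**Which contrast does the text point to?** The interaction term and the by-visit plots of means with 90% intervals belong together. No visible sentence mentions an overall diary effect, an average over visits or equal weights.

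**The case for a change.** The strongest reply is that the by-visit wording belongs to the plots only. The same two reporting sentences, on intervals and P-values and then on plots by visit, also appear under Primary Efficacy Analyses, where the model has no visit factor. The wording alone therefore cannot settle which diary contrast is tested. Even with by-visit reporting, the week 1 result changes meaning with the window. Seven diary variables are listed as secondary, so windows chosen after unblinding would leave some room for selection.

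Part of this stands. The two gaps are real in the visible text, and the sentences on the model and the P-values are not themselves blacked out. The repeated wording does weaken the inference from the plots, although a treatment-by-visit interaction appears only in the diary model, and its usual purpose is to give contrasts at each visit. The room for selection is small: one of four contrasts per dose moves, and the contrasts on either side of it, which do not depend on the choice, would be reported with it. The visible text is also a synopsis, where night windows are often left out, and the blocks that follow cannot be read.

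**Conclusion.** The concern does not call for a change. The figures of 25.0% and 32.1% are arithmetically right, but they describe an equal-weight overall diary estimate that the plan does not state. They would matter only if such an estimate were reported, with equal weights, and if the effect on nights 1-2 differed from that on later nights. Even then the departure from the 21-night mean is 15.5% to 22.6% of that difference.

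On the natural by-visit reading, what is left is the label on one contrast, worth 2/7 of the same difference. A separate early level is reasonable in itself, because it lines up with the first on-treatment polysomnography pair. Night windows must be fixed before the diary tables can be programmed, and either choice gives an interpretable result once the tables show it.

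This conclusion rests on by-visit reporting and on a covariance that lets the overlapping levels correlate freely. The visible text supports the first and is silent on the second. The endpoints are secondary, and the primary WASO analysis and its power are unaffected.

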Full Title of the Study: A Phase 2, Randomized, Double-Blind, Multi-Center, Placebo-Controlled, Parallel-Group Study to Evaluate the Safety, Tolerability, and Efficacy of V117957 in Subjects with an Alcohol Use Disorder who are Experiencing Insomnia Associated with Alcohol Cessation	
Investigator(s)/Center(s): 20 sites	
Planned First Subject First Visit: 3Q2019	Phase of Development: Phase 2
Objectives:	
Primary: To evaluate the safety, tolerability, and efficacy of V117957 in subjects with an alcohol use disorder, who experience insomnia associated with alcohol cessation, compared to placebo.	
Secondary: Assess sleep components as measured by polysomnography, assess self-reported sleep outcomes measured by patient diary, and assess next day residual effects of study drug. [REDACTED] [REDACTED]	
Study Design (Methodology): This is a phase 2, randomized, double-blind, multi-center, placebo-controlled, parallel-group study in subjects with an alcohol use disorder (AUD), who are experiencing insomnia associated with alcohol cessation (IAAC). The total duration of the study for a given subject is up to 59 days inclusive of a 21-day screening period, 21-day treatment period, 3-day washout period, and follow-up period of up to 14 days. During the screening period subjects will be assessed to determine eligibility for enrollment in the study. Subjects complete the Consensus Sleep Diary-Morning (CSD-M) at home and if at least 3 nights of any 7-night period indicate insomnia, they will enter a sleep lab for 2 consecutive nights of polysomnography (PSG) evaluation. During the treatment period, eligible subjects will be randomly assigned to V117957 1 mg QHS, V117957 2 mg QHS or placebo QHS (approximately 50 per arm, in a 1:1:1 ratio). Eligible subjects will be required	

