The washout period includes an assessment of vital sign measurements, AEs and concomitant medications. The CSD-M, DSST, KSS, POMS-Brief and C-SSRS will be completed. Study drug treatment and PSG assessments will be performed.

The end of treatment (EOT) visit consists of weight, physical and neurological exams, serum pregnancy test, C-SSRS, HADS, drug and alcohol screen, ECG, vital sign measurements, AEs and concomitant medications, CSD-M, [REDACTED] PSG, DSST, KSS, POMS-Brief, and clinical laboratory assessments.

Follow up:

The end of study visit will occur approximately 7 days after the last double-blind treatment dose and consists of vital signs, assessment of AEs and conmeds, CSD-M [REDACTED].

A follow up phone call approximately 7 days after the EOS visit will consist of an assessment of AEs and concomitant medications.

Criteria and Methods for Evaluation:

Primary Efficacy Variable:

The primary efficacy variable will be derived using 2 consecutive nights of data from polysomnography (PSG):

- Change from baseline of wakefulness after sleep onset (WASO) measured by PSG

Secondary Efficacy Variables:

The secondary efficacy variables will be derived from PSG recordings as well as CSD-M (sleep diary) data:

- SE: Sleep efficiency
- LPS: Latency to persistent sleep
- TST: Total sleep time
- NAW: Number of awakenings

The secondary efficacy variables derived from the CSD-M (sleep diary) include the following:

- sSleep: subject estimated sleep quality
- sTST: subject estimated amount of time spent asleep
- sWASO: subject estimated minutes of wakefulness during the night after initial sleep onset
- sSOL: subject estimated minutes from lights off to sleep onset
- sSE: subject estimated proportion of time spent asleep per time spent in bed derived from sTST divided by sTIB

- sNAW: subject estimated number of awakenings
- subject estimated morning sleepiness on awakening

Additional secondary efficacy variables:

- Proportion of responders derived from PSG [REDACTED]
- Rebound insomnia endpoints [REDACTED] during the washout/follow-up period

Pharmacodynamic Variables:

[figure not shown]
The pharmacodynamic variables assessing next-day residual effects:

- DSST: Digit Symbol Substitution Test
- KSS: Karolinska Sleepiness Scale
- POMS-Brief: Profile of Mood States- Brief

Safety Variables:

The safety variables assessing safety and tolerability of V117957:

- Adverse events.

Efficacy Analysis:

Analysis Populations

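### The diary MMRM has no baseline-by-visit term, so the week 3 dose-placebo contrast can be modestly biased if the baseline slope changes over visits and drop-out also differs between arms

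*Combined protocol and SAP*

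**What the plan says.** The model is in the Synopsis of the combined protocol and SAP, under Secondary Efficacy Analyses.

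- It is introduced with "For CSD-M sleep diary data which will be processed into weekly data", and the outcome is change from baseline.
- The time factor is "visit (first 2 nights, week 1, week 2, and week 3", so it has four levels.
- The factors are age group, treatment and visit, followed by "and treatment-by-visit interaction as fixed effects, and baseline measurement as a covariate". No baseline-by-visit term is listed.
- The output is stated as "90% confidence intervals (CIs) and P-values comparing placebo and each V117957 dose will be summarized".

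The endpoints are secondary: the list opens "The secondary efficacy variables derived from the CSD-M (sleep diary) include the following" and includes sWASO, sTST and sSOL. The planned number of subjects is "approximately 150 (~50 per treatment group) to ensure at least 30 subjects per group complete treatment". The only missing-data sensitivity work mentioned is optional, names no method, and stands under the primary PSG analysis.

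**The concern.** The plan allows the treatment effect to vary by visit but assumes, without giving a reason, that the effect of baseline does not. The periods differ in setting and in distance from baseline: the first 2 nights are spent in the sleep lab, while the weekly periods are mostly at home and progressively later. Subjects are also selected on poor diary nights, so regression to the mean is expected, and it need not be the same in every period.

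If the slope does change, a single slope is wrong at week 3. Cumulative loss is greatest there, and the sample size tolerates a good deal of it. If the subjects remaining in the arms then differ in baseline, the adjustment for that difference uses the wrong slope, and the error goes into the estimated treatment effect.

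**Working it through.** **The plan's own figures.** With 30 per group, a difference of 30 min and SD 45 min, the standard error is 45 × √(2/30) = 11.62 and 30/11.62 = 2.58. One-sided 5% power is Φ(2.58 − 1.645) = 0.826, or 0.818 by the noncentral t with 58 df. The stated >80% reproduces. The drop-out allowance is 1 − 30/50 = 40%. This is the most that is tolerated, not an expected rate.

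**Inputs.** From the documents: four visit levels, 1:1:1 allocation with about 50 per arm, and 90% intervals. Not in the documents, hence assumed: diary SD 45 min at baseline and after (the 45 in the plan is for PSG WASO), residual correlation 0.6 per visit step, unstructured covariance, monotone drop-out, the baseline slopes, and the link between drop-out and baseline. Slopes below are of the post-baseline value on baseline; the slope of change on baseline is that value minus 1.

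**Mechanism, roughly.** Take slopes falling from 0.7 to 0.5, with drop-out linked to baseline in placebo only. Among week 3 completers, baseline is about 15 min higher on active than on placebo. The fitted common slope is about 0.64 (from the run with completely random drop-out), against a true 0.5 at week 3. The error is about (0.5 − 0.64) × 15 = −2.1 min. The full model gives −1.7; it also draws on earlier visits, so the two need not agree exactly.

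**Bias at week 3.** Entries are the model as written minus the model with baseline-by-visit, in minutes, from 300,000 simulated subjects per scenario. Drop-out is 40% unless stated, and the odds ratio for drop-out is 2.7 per baseline SD. A negative value favours the drug on a wake-time scale.

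| Drop-out pattern | Constant 0.6 | 0.7 to 0.5 | 0.8 to 0.4 | 0.9 to 0.3 |
|---|---|---|---|---|
| Same rate and relation in all arms | 0.0 | −0.0 to +0.1 | −0.0 to +0.1 | −0.0 to +0.1 |
| Same relation; placebo 40%, active 20% | 0.0 | −0.8 | −1.6 | −2.4 |
| Related to baseline in placebo only | 0.0 | −1.7 | −3.7 | −5.7 |
| Opposite directions by arm | 0.0 | −3.8 | −7.6 | −11.8 |

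With the interaction, bias was within about 0.5 min (simulation noise) throughout. Variations on the placebo-only row, for the slope patterns 0.7 to 0.5 and 0.8 to 0.4:

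- 20% drop-out: −1.0 and −1.9.
- Log-odds of drop-out 0.5 per SD instead of 1: −1.0 and −2.0; at 20% drop-out, −0.5 and −1.0.
- Diary SD 30 to 60: −1.2 to −2.4 and −2.5 to −5.2.

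A second set of simulations used different inputs: 1,500 trials, 50 per arm, residual SD 38, true effect −20 min, and slope of change moving from −0.3 to −0.6. With placebo-only drop-out it gave −23.3 as written and −19.9 with the interaction. With the link in the active arm only, the shift reverses to about +3.3 min. With mild slopes (of change, −0.4 to −0.5) and one-arm drop-out, the shift is about 0.5 to 1.2 min.

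**Precision at week 3.** Model standard errors, N = 150, completely random 40% drop-out:

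| Slopes | As written | With interaction | Ratio |
|---|---|---|---|
| Constant 0.6 | 8.91 | 8.90 | 1.00 |
| 0.7 to 0.5 | 9.75 | 9.63 | 1.01 |
| 0.8 to 0.4 | 10.82 | 10.23 | 1.06 |
| 0.9 to 0.3 | 12.21 | 10.68 | 1.14 |

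**What the bias means for error rates.** For the two middle slope patterns with placebo-only drop-out, 1.7/9.75 = 0.17 and 3.7/10.82 = 0.34 standard errors. A nominal one-sided 5% error becomes Φ(−1.645 + 0.17) = 7.0% and Φ(−1.645 + 0.34) = 9.6%.

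**The case against.** A reader might infer that the common slope biases week 3 whenever drop-out is related to baseline severity, and that it always costs precision. Neither follows. With the same rate and relation in all arms, the contrast shifts by at most 0.1 min for every slope pattern tried. With equal slopes, the planned model is as precise as the alternative or slightly more so: empirical SD 8.91 against 9.08 in the second set of simulations.

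It is also tempting to argue that a 2-night mean and a weekly mean must have different slopes because one is noisier. That is not so. The slope is Cov(Y, B)/Var(B), and extra noise in Y changes the residual variance, not the slope. Only a real change in covariance with baseline, through setting or elapsed time, moves it. The documents give no evidence that this happens or by how much.

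Three further limits stand. The sizes rest on assumed slopes and drop-out links. Minutes do not describe sleep quality, sNAW, sSE or morning sleepiness. The plan does not single out week 3; it is used here because cumulative loss is greatest then.

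Finally, the visible model is in a synopsis and redacted lines follow it, so further detail may exist. The model sentence itself is complete, however, and as it stands it implies one slope.

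These arguments limit the size and the conditions of the problem. They are not a reason to keep the equal-slope assumption when dropping it costs so little.

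**Conclusion.** The point holds in a limited form. As written, the diary MMRM assumes one baseline slope for four unlike periods. Bias at week 3 needs both a slope that changes over visits and drop-out that differs by arm in rate or in relation to baseline. For minute-scale endpoints it is then about 0.5 to 4 min in mild to strong scenarios at diary SD 45 min and up to 40% drop-out. That is well under half of a week 3 standard error of about 9 to 11 min, and the sign depends on which arm loses which subjects. Larger values need a steep slope change, opposite drop-out patterns or a larger SD.

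The documents do not support a claim that bias is likely, that it favours the drug, or that 40% loss is expected. Confidence in the mechanism is high; confidence in the size is limited by the assumptions. Only secondary endpoints are touched.

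**What to change.** In the Synopsis, Secondary Efficacy Analyses, add baseline-by-visit to the diary MMRM. The fixed effects become age group, treatment, visit, treatment-by-visit, baseline and baseline-by-visit, with the rest as planned. Make the same change wherever the full diary model is written out, and make it before unblinding so that it is not a post-hoc choice.

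The cost is 4 − 1 = 3 degrees of freedom, one term in the text and the program, and no new data. If the slopes are in fact equal, the standard error is about 0 to 3% larger: no increase under random drop-out, 9.08/8.91 = 1.02 in the second set of simulations, and 1/0.97 = 1.03 when arms drop out differently.
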